Baseline Visit: At UW SLU, lasts about 7-8 hours. Includes Indirect calorimetry, DXA, fasting blood draw, measurements such as weight, waist and hip, neck, blood pressure, heart rate and temperature, behavioral questionnaires, an MRI followed by a snack (milk, crackers, nut butter) equivalent to about 20% of the individual's daily needs. A second MRI followed by buffet provided by Fred Hutch Human Nutrition Lab will occur. SWL and BWL subjects will be given the smart scale at this visit. SWL will have only the first MRI, no snack or buffet so the Baseline visit should take about 3-4 hours.

Interim Visit: HWC participants will not have this visit. The Smart scale will automatically transmit weights to research staff. Once the subject is close to 7% weight loss, the Interim Visit will be scheduled. Takes place at UW SLU, lasts about 3-4 hours. Includes measurements such as weight. Fasting blood draw, MRI and DXA scan. The time to 7-8% weight loss is anticipated to vary between the SWL and BWL arm. We anticipate this level of weight loss will be achieved by 75% in the BWL arm by 16–20 wk. and by most SWL participants within the first 2–6 weeks. Subjects who don't achieve 7-8% weight loss may still have this visit prior to the 6-month visit (approximately 5-month time point), or they may not be scheduled for this visit. Visits for normal weight controls will occur 3 mo. after their baseline visit.

At approximately the 3 month time-point, (about 3 months after baseline visit), subjects will receive 3 unannounced 24-hour dietary recalls (ASA-24) via email. Each dietary recall takes about 20-40 minutes to complete.

6- Month Visit: Same as Baseline Visit.

12- Month Visit and 18-Month Visits: Like Interim Visit in length and procedures. We will take waist and hip measurement and vitals at 18-month visit.

Procedure	IP Screening	Baseline	% Wt Change	6 month	12 month	18 month
Physical Exam (BWL only)	x					
Medical History	x	x	x	x	x	x
Anthropometrics						
Height	x	—	—	—	—	—
Weight	x	x	x	x	x	x
Waist	—	x	—	x	—	x
Hip	—	x	—	x	—	x
Neck	—	x	—	—	—	—
Vitals (BP, HR)	x	x	—	x	—	x
Blood Draw						
Non-Fasting	x	—	—	—	—	—
Fasting ¹	—	x	x	x	x	x
Fasting ²	—	x	—	x	—	—
DNA	—	x	—	—	—	—
iDXA		x	x	x	x	x
MRI (glosis)	x	x	x	x	x	x
Activity Monitor*	x		x			
Diet Recall* (ASA24) ^{3x}	x	**	x			
Indirect Calorimetry	x		x			
Questionnaires						
MRI Safety Qx	x	x	x	x	x	x
Participant QxVHT	x	—	—	—	—	—
PAQ	x	—	—	—	—	—
QEWP	—	x	—	—	—	—
EHI	—	x	—	—	—	—
STOP-BANG	—	x	—	—	—	—

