STAI-Trait	—	x	—	—	—	—
STAI-State ^{2x}	—	x	—	x	—	—
PHQ-9	—	x	—	x	—	—
PSQI	—	x	—	x	—	—
TFEQ	—	x	—	x	—	—
Appetite Ratings (VAS) ^{8x}	x		x			
Appeal Ratings ^{2x}	x		x			
MRI Pre-meal	x		x			
Standardized Meal	x		x			
MRI Post-meal	x		x			
Ad Libitum Buffet Meal	x		x			

* MRI pre-meal, standardized meal, MRI post-meal and *ad libitum* buffet meal are for the HWC and BWL groups only.

Below is a description of study procedures in more detail.

Physical examination. Height, weight, and vital signs will be obtained. A physical examination will be performed by study physicians. We will add temperature to the vitals at In-Person Screening, Baseline, 6M, 18M.

Body composition. Women of child-bearing potential will undergo a pregnancy test prior to receiving the DXA scan. Subject will change into scrubs. Certified DXA technicians will perform whole body scans for computing total body fat and lean mass (Lunar iDXA, GE Healthcare). CoreScan software will calculate visceral fat content, and its algorithm provides comparable results to abdominal CT scans. DXA takes about 30 minutes.

Questionnaires. Participants will self-report lifetime maximum weight and a detailed weight history (Participant Questionnaire). Descriptive measures will include the Three-Factor Eating Questionnaire (R-18), Questionnaire on Eating and Weight Patterns-Revised (binge eating disorder screening), Edinburgh Handedness Inventory, and Pittsburgh Sleep Quality Index, IPAQ, STOP-BANG, STAI-Trait, STAI-State, PHQ-9, Pregnancy history and Actigraph logs. Time to complete questionnaires should be about 15-20 minutes. At Baseline and 6-month visits subjects will be given VAS appetite ratings about every 30 minutes. Subjects will also be given taste and appeal ratings at Baseline and 6-month visits before and/or after meals and MRIs. An Exit Survey will be given to subjects at the end of the Behavioral Weight Loss Intervention. The survey will be uploaded to Zipline. We will administer questionnaires on paper, ipad, emailed questionnaire, or REDCap as needed to maintain safe distance and to comply with COVID related requirements.

Physical Activity. Participants will wear accelerometers for 7 days (ActiGraph). Valid data will require at least 5 days of >10 h of wear time. Average duration of sedentary time and light, moderate, and vigorous physical activity will be calculated using standardized software.

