2. Study Procedures. Potential risks include 1) anxiety and embarrassment as a result of completing the medical history, physical examination, or other self-reported measures; 2) pain, minor injury (bruising), or the development of a localized inflammation (thrombophlebitis) from obtaining blood samples. Occasionally people feel faint or nauseous during blood draw; 3) intake of a mandatory amount of a standardized snack that may in rare cases cause discomfort, nausea, vomiting, or a reaction from an unidentified food allergy or sensitivity; and 4) discomfort from hunger due to fasting or hypoglycemia due to fasting.

DXA scan: There are some risks from the DXA scan you will undergo during this study. This scan will expose you to radiation. If you live in the US, you receive about 3 millisieverts of radiation each year. It comes from space and the earth around you. This is called “background radiation.” A “millisievert” (mSv) is a unit used to measure doses of radiation. The radiation dose to your whole body from your DXA scan will be less than 0.01 mSv. The risk of harm from this amount of radiation is very low. If you have more procedures that expose you to radiation, this risk will go up. The radiation from x-rays and scans may be harmful to a fetus. If you are a woman who could become pregnant, you must have a pregnancy test done before your DXA scan. If you are pregnant you may not take part in this study.

3. *Symptomatic Hypotension*: Weight loss may reduce blood pressure.

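### In the lifestyle arm (BWL), blood pressure and heart rate could cheaply be added to the Interim visit: none is scheduled between Baseline and 6 months, although symptomatic hypotension is a named risk (minor)

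*Protocol*

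**What the plan says.** Protocol section 5.1 describes the Interim visit in these words: "Takes place at UW SLU, lasts about 3-4 hours. Includes measurements such as weight. Fasting blood draw, MRI and DXA scan". Its trigger is weight, transmitted by the smart scale: "Once the subject is close to 7% weight loss, the Interim Visit will be scheduled". On timing, the Protocol says: "We anticipate this level of weight loss will be achieved by 75% in the BWL arm by 16–20 wk". BWL participants who fall short may be seen at about month 5, "or they may not be scheduled for this visit".

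The procedure table has six visit columns: in-person screening, Baseline, percent weight change (the Interim visit), 6, 12 and 18 months. Its vitals row reads "Vitals (BP, HR) x x — x — x".

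The 12- and 18-month visits are modelled on the Interim visit, with one addition: "We will take waist and hip measurement and vitals at 18-month visit". The Physical examination paragraph says: "We will add temperature to the vitals at In-Person Screening, Baseline, 6M, 18M". The 6-month visit repeats Baseline, where blood pressure and heart rate are measured.

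Section 10.1 item 3 is headed Symptomatic Hypotension and consists of one sentence: "Weight loss may reduce blood pressure". The form's instruction for that section asks how each risk will be managed or reduced. Section 10.5 says there will be a Safety Monitor and a DSMP uploaded separately.

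**The concern.** In BWL the weight loss is produced by the research itself. Section 1.6 says the lifestyle program is part of the study, and section 5.1 sets a 10% loss goal over 6 months with increased physical activity. Section 2.2 excludes poorly controlled hypertension and readings above 160/100 but not controlled hypertension, so someone on blood pressure treatment could enroll. The investigators themselves list a fall in blood pressure as a risk of losing weight.

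The schedule reads blood pressure at Baseline and again at 6 months, when the program ends. Between those points the participant comes on site for several hours, at a moment defined by substantial weight loss, and no cuff reading is scheduled. A low reading found then could still change how the rest of the program is handled. One found at 6 months cannot.

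This is a participant-safety matter only. Neither objective in section 1.5 and no outcome in the SAP uses blood pressure.

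The surgical arm has the same dash but is left out. Its weight loss comes from clinical surgery, and the section 10.1 instruction excludes risks of non-research procedures.

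**Working it through.** The Protocol states no figure for this point, so there is none to reproduce. The check has three parts.

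**1. Is a reading really unscheduled at the Interim visit?** Four places in section 5.1 bear on this.
- Vitals row, in column order: screening yes, Baseline yes, Interim dash, 6 months yes, 12 months dash, 18 months yes. All six cells are filled, so the dash is not a gap left by text extraction.
- Interim visit text: weight, fasting blood, MRI and DXA are named; blood pressure and heart rate are not. The wording on measurements is open-ended and could not settle the question alone.
- 12- and 18-month text: both follow the Interim pattern, and vitals are then added for 18 months. The addition would be unnecessary if the Interim pattern already included them.
- Physical examination paragraph: the visits listed for vitals are screening, Baseline, 6 months and 18 months.

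The four agree. No blood pressure or heart rate reading is scheduled between Baseline and 6 months.

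**2. How much earlier would an Interim reading come?**

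Inputs from the Protocol: 75% of BWL expected to reach 7-8% loss by 16-20 weeks (section 5.1); at most 100 BWL participants (section 2.7); a 10% loss goal (section 5.1).

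Assumptions: 6 months is week 26; month 5 is 5 × 52/12 = 21.7, about week 22; the Interim visit takes place about when 7-8% loss is reached.

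- Gap between scheduled readings: Baseline to week 26, about 26 weeks.
- Threshold reached at week 20: 26 − 20 = 6 weeks earlier.
- Threshold reached at week 16: 26 − 16 = 10 weeks earlier.
- Visit held at about month 5 for someone below 7-8%: 26 − 22 = 4 weeks earlier.
- Participants expected to reach the threshold: 0.75 × 100 = 75 at most.
- Remaining participants: 100 − 75 = 25 at full enrollment; they may have a month-5 visit or none.
- Share of the goal already lost at the Interim visit: 7/10 = 70% to 8/10 = 80%.

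The 6 to 10 weeks can be wrong in either direction. The 16-20 weeks is when the loss is expected to have been reached, so some participants will get there sooner and gain more time. A delay between reaching the threshold and attending the visit shortens the lead.

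**3. Do other contacts supply a reading?** Medical history is taken at every visit, including the Interim visit. The BWL sessions run weekly to week 12 and then about every other week, possibly by Zoom or telephone. Either contact could bring out symptoms, but neither is described as including a blood pressure measurement. The BWL physical examination takes place at screening, before weight loss begins.

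**The case against.** The strongest reply is that the named risk is symptomatic hypotension, and symptoms already have routes to staff: the medical history at each visit and frequent sessions with the interventionist. Nothing in the documents shows that these would miss symptoms, and one cuff reading around weeks 16 to 20 may add little. The screening examination, the physician's discretion to exclude anyone for whom participation is unsafe, and the Safety Monitor are also real safeguards. Several other entries in section 10.1 are just as brief, so the one-sentence entry may be only how the form was filled in.

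Most of this stands, and it is why the point is minor. What survives is narrow: none of these safeguards is described as giving a blood pressure reading while weight is being lost, and the reading is nearly free at a visit already held on site.

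A reader might also infer that the study has no plan for hypotension and that participants are not told what to report. The documents do not support that. The DSMP is a separate upload that was not supplied, and consent pages were removed before review; either may cover both matters. A reader might likewise take 6 weeks as a guaranteed minimum lead, or 75 as the expected number. The first holds only if the visit coincides with the weight threshold. The second is a ceiling, because 100 is the maximum planned.

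**Conclusion.** The point holds as a minor, inexpensive safety improvement for BWL. The schedule contains no blood pressure or heart rate reading between Baseline and 6 months, and the Interim visit is a natural place for one. The gain is a reading roughly 6 to 10 weeks earlier for up to about 75 of at most 100 participants. This rests on week 26 for the 6-month visit, on the Protocol's own forecast of 75% reaching 7-8% loss by 16-20 weeks, and on the visit falling close to that moment.

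No harm is quantified. The documents give neither a rate of hypotension nor the number of participants on blood pressure treatment, so no count of events prevented can be offered. The analysis is unaffected. The conclusion concerns the visit schedule and section 10.1 only.

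**What to change.** - In the section 5.1 procedure table, change the vitals dash in the percent weight change column to a scheduled measurement, and add blood pressure and heart rate to the Interim visit text.
- Have the study physician set a threshold in advance. Send any reading below it, and any low-blood-pressure symptom reported (for example in the medical history already taken at that visit), to the study physician. Without a stated threshold, staff could not apply the rule consistently.
- In section 10.1 item 3, cite this arrangement as the way the risk is managed. If the DSMP already sets out a response to hypotension, cite that instead of duplicating it.

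The cost is a few minutes per Interim visit, using measurements already made at Baseline and 6 months, and a small IRB modification. No extra visit is needed.

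The fix is partial. Participants with no Interim visit, or a remote one, get no reading. A single reading can miss intermittent hypotension. The interval from Baseline to about 7% loss stays without a reading.

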6.1 Involvement of minors. Does your research include minors (children)?

Minor or child means someone who has not yet attained the legal age for consent for the research procedures, as described in the applicable laws of the jurisdiction in which the research will be conducted. This may or may not be the same as the definition used by funding agencies such as the National Institutes of Health.

- In Washington State the generic age of consent is 18, meaning that anyone under the age of 18 is considered a child.
- There are some procedures for which the age of consent is much lower in Washington State. See the [WORKSHEET: Children](#) for details.
- The generic age of consent may be different in other states, and in other countries.

	No
	Yes

No → If no, go to [Section 8](#).

Yes → If yes, provide the age range of the minor subjects for this study and the legal age for consent in your population(s). If there is more than one answer, explain.

Don't know

→ This means it is not possible to know the age of your subjects. For example, this may be true for some research involving social media, the Internet, or a dataset that you obtain from another researcher or from a government agency. Go to [Section 8](#).

6.2 Parental permission. Parental permission means actively obtaining the permission of the parents. This is not the same as “passive” or “opt out” permission where it is assumed that parents are allowing their children to participate because they have been provided with information about the research and have not objected or returned a form indicating they don’t want their children to participate.

a. Will you obtain parental permission for:

 All of your research procedures	→ Go to question 6.2b.
 None of your research procedures	→ Use the table below to provide your justification, and skip question 6.2b.
 Some of your research procedures	→ Use the table below to identify the procedures for which you will not obtain written parental permission.

Be sure to consider all research procedures and plans, including screening, future contact, and sharing/banking of data and specimens for future work.

Children Group ¹	Describe the procedures or data/specimen collection (if any) for which there will be NO parental permission	Reason why you will not obtain parental permission	Will you inform them about the research? ²	
			YES	NO
				
				
				
				
				
				

Table footnotes

1. If your answer is the same for all children groups or all procedures, you can collapse your answer across the groups and/or procedures.
2. Will you inform them about the research beforehand even though you are not obtaining active permission?

b. Indicate by checking the appropriate box(es) your plan for obtaining parental permission

 Both parents, unless one parent is deceased, unknown, incompetent, or not reasonably available; or when only one parent has legal responsibility for the care and custody of the child
 One parent, even if the other parent is alive, known, competent, reasonably available, and shares legal responsibility for the care and custody of the child.

This is all that is required for minimal risk research.

If you checked both boxes, explain:

6.3 Children who are wards. Will any of the children be wards of the State or any other agency, institution, or entity?

 No
 Yes

→ If yes, an advocate may need to be appointed for each child who is a ward. The advocate must be in addition to any other individual acting on behalf of the child as guardian or in loco parentis. The same individual can serve as advocate for all children who are wards.

Describe who will be the advocate(s). Your answer must address the following points:

- Background and experience
- Willingness to act in the best interests of the child for the duration of the research
- Independence of the research, research team, and any guardian organization

7 ASSENT OF CHILDREN (MINORS)

Go to [Section 8](#) if your research does not involve children (minors).

7.1 Assent of children (minors). Though children do not have the legal capacity to “consent” to participate in research, they should be involved in the process if they are able to “assent” by having a study explained to them and/or by reading a simple form about the study, and then giving their verbal choice about whether they want to participate. They may also provide a written assent if they are older. See [WORKSHEET: Children](#) for circumstances in which a child’s assent may be unnecessary or inappropriate.

a. Will you obtain assent for:

All of your research procedures and child groups

→ Go to [question 7.2.](#)

None of your research procedures and child groups

→ Use the table below to provide your justification, then skip to question 7.5.

Some of your research procedures and child groups

→ Use the table below to identify the procedures for which you will not obtain assent.

Be sure to consider all research procedures and plans, including screening, future contact, and sharing/banking of data and specimens for future work.

Children Group ¹	Describe the procedures or data/specimen collection (if any) for which assent will NOT be obtained	Reason why you will not obtain assent

Table footnotes

1. If your answer is the same for all children groups or all procedures, you can collapse your answer across the groups and/or procedures.

7.2 Assent process. Describe how you will obtain assent, for each child group. If your research involves children of different ages, answer separately for each group. If the children are non-English speakers, include a description of how you will ensure that they comprehend the information you provide.

7.3 Dissent or resistance. Describe how you will identify a child's objection or resistance to participation (including non-verbal indications) during the research, and what you will do in response.

7.4 Documentation of assent. Which of the following statements describes whether you will obtain documentation of assent?

 None of your research procedures and child groups	→ Use the table below to provide your justification, then go to question 7.4.a.
 All of your research procedures and child groups	→ Go to question 7.4.a , do not complete the table
 Some of your research procedures and/or child groups	→ Complete the table below and then to go question 7.4.a

Children Group ¹	Describe the procedures or data/specimen collection (if any) for which assent will NOT be documented	Reason why you will not document assent

Table footnotes

1. If your answer is the same for all children groups or all procedures, you can collapse your answer across the groups and/or procedures.

a. Describe how you will document assent. If the children are functionally illiterate or are not fluent in English, include a description of what you will do.

b. Upload all assent materials (talking points, videos, forms, etc.) to the Consent Form and Recruitment

Materials SmartForm of Zipline. Assent materials are not required to provide all of the standard elements of adult consent; the information should be appropriate to the age, population, and research procedures. The documents should be in Word, if possible.

7.5 Children who reach the legal age of consent during participation in longitudinal research.

Children who were enrolled at a young age and continue for many years: It is best practice to re-obtain assent (or to obtain it for the first time, if you did not at the beginning of their participation).

Children who reach the legal age of consent: You must obtain informed consent from the now-adult subject for (1) any ongoing interactions or interventions with the subjects, or (2) the continued analysis of specimens or data for which the subject's identify is readily identifiable to the researcher, unless the IRB waives this requirement.

a. Describe your plans (if any) to re-obtain assent from children.

b. Describe your plans (if any) to obtain consent for children who reach the legal age of consent.

- If you plan to obtain consent, describe what you will do about now-adult subjects whom you are unable to contact.
- If you do not plan to obtain consent or think that you will be unable to do so, explain why.

7.6 Other regulatory requirements. (This is for your information only; no answer or response is required.)

Researchers are responsible for determining whether their research conducted in schools, with student records, or over the Internet comply with permission, consent, and inspection requirements of the following federal regulations:

- PPRA – Protection of Pupil Rights Amendment
- FERPA – Family Education Rights and Privacy Act
- COPPA – Children's Online Privacy Protection Act

8 CONSENT OF ADULTS

Review the following definitions before answering the questions in this section.

CONSENT is the process of informing potential subjects about the research and asking them whether they want to participate. It usually (but not always) includes an opportunity for subjects to ask questions. It does not necessarily include the signing of a consent form. This question is about the consent process.

CONSENT DOCUMENTATION refers to how a subject's decision to participate in the research is documented. This is typically obtained by having the subject sign a consent form.

CONSENT FORM is a document signed by subjects, by which they agree to participate in the research as described in the consent form and in the consent process.

ELEMENTS OF CONSENT are specific information that is required to be provided to subjects.

PARENTAL PERMISSION is the parent's active permission for the child to participate in the research. Parental permission is subject to the same requirements as consent, including written documentation of permission and required elements.

SHORT FORM CONSENT	is an alternative way of obtaining written documentation of consent that is most commonly used with individuals who are illiterate or whose language is one for which translated consent forms are not available.
WAIVER OF CONSENT	means there is IRB approval for not obtaining consent or for not including some of the elements of consent in the consent process.
WAIVER OF DOCUMENTATION OF CONSENT	means that there is IRB approval for not obtaining written documentation of consent.

8.1 Groups Identify the groups to which your answers in this section apply.

Adult subjects

Parents who are providing permission for their children to participate in research

→ If you selected PARENTS, the word "consent" below should also be interpreted as applying to parental permission and "subjects" should also be interpreted as applying to the parents.

8.2 The consent process. This series of questions is about whether you will obtain consent for all procedures except recruiting and screening and, if yes, how.

The issue of consent for recruiting and screening activities is addressed in [question 4.6](#). You do not need to repeat your answer to question 4.6.

a. Are there any procedures for which you will not obtain consent?

No

Yes → If yes, use the table below to identify the procedures for which you will not obtain consent. "All" is an acceptable answer for some studies.

Be sure to consider all research procedures and plans, including future contact, and sharing/banking of data and specimens for future work.

Group ¹	Describe the procedures or data/specimen collection (if any) for which there will be NO consent process	Reason why you will not obtain consent	Will you provide subjects with info about the research after they finish?	
			YES	NO
				
				
				
				
				

Table footnotes

1. If your answer is the same for all groups you can collapse your answer across the groups and/or procedures.

b. **Describe the consent process**, if you will obtain consent for any or all procedures, for any or all groups. Address groups and procedures separately if the consent processes are different.

Be sure to include:

- The location/setting where consent will be obtained
- Who will obtain consent (refer to positions, roles, or titles, not names).
- Whether/how you will provide an opportunity for questions
- How you will provide an adequate opportunity for the subjects to consider all options

Consent will occur in person or remotely. The research staff (research coordinator or assistant) will consent the subjects. Subjects will have the opportunity to ask questions or for clarification at any time during or after informed consent, either in person during the visits or over the phone or email. We will provide a blank copy of the consent form to participants by mail, email, in REDCap or screenshare in Zoom. We will schedule a call or Zoom to review the consent form and answer questions. The participant could sign and photograph the signature page and text, email or mail the signed consent page, or use DocuSign or REDCap. Participants could also sign the consent form at the in-person screening visit prior to doing research procedures.

We will re-consent enrolled participants from whom we want to draw additional blood. We will email or call enrolled participants when they are due to schedule their next visit. We will let them know of the changes to the study visits and consent form including that we would like to draw an additional tube of about 30 mL of blood at one of their remaining visits. We will provide a copy of the consent form to the participant via email or mail or via a link to REDCap so that the participant can review the changes made to the consent form. We will talk through the consent form changes with the participant over the phone or via Zoom. We will answer questions the participant may have about the changes and let them know they can decline to have the additional 30 mL of blood drawn. We will ask the participant to sign the new consent form as described in the previous paragraph (sign a paper copy and take a photo or scan and text or email it back to us, or mail it back in an envelope we provide at the time of the visit before they begin procedures, or DocuSign or REDCap or sign the consent form in person before beginning research procedures at the visit).

c. **Comprehension**. Describe how you will ensure or test the subjects' understanding of the information during the consent process.

If subjects seem like they do not understand what is being asked of them, they will not be consented for the study. We will ask subjects to explain what they are being asked to do if they join the study. If unable to articulate this, we will not consent the subject.

d. **Influence**. Does your research involve any subject groups that might find it difficult to say "no" to your research because of the setting or their relationship with you, even if you don't pressure them to participate?

Examples: Student participants being recruited into their teacher's research; patients being recruited into their healthcare provider's research, study team members who are participants; outpatients recruited from an outpatient surgery waiting room just prior to their surgery.

No

Yes

→ If yes, describe what you will do, for each of these subject groups, to reduce any effect of the setting or relationship on their decision.

Examples: a study coordinator will obtain consent instead of the subjects' physician; the researcher will not know which subjects agreed to participate; subjects will have two days to decide after hearing about the study.

Some subjects could be patients of the PI. The PI will not approach patients about the study. Only research coordinators will approach and screen potential subjects about participating.

e. **Ongoing process.** For research that involves multiple or continued interaction with subjects over time, describe the opportunities (if any) you will give subjects to ask questions or to change their minds about participating.

If subjects cannot or do not want to return for visits, that is their choice.

8.3 Written documentation of consent. Which of the statements below describe whether you will obtain documentation of consent? NOTE: This question does not apply to screening and recruiting procedures which have already been addressed in [question 4.6](#).

Documentation of consent that is obtained electronically is not considered written consent unless it is obtained by a method that allows verification of the individual's signature. In other words, saying "yes" by email is rarely considered to be written documentation of consent

a. Are you obtaining written documentation of consent for:

None of your research procedures → Use the table below to provide your justification then go to [question 8.4](#).

All of your research procedures → Do not complete the table; go to [question 8.3.b](#).

Some of your research procedures → Use the table below to identify the procedures for which you will not obtain written documentation of consent from your adult subjects.

Adult subject group ¹	Describe the procedures or data/specimen collection (if any) for which there will be NO documentation of consent	Will you provide them with a written statement describing the research (optional)?	
		YES	NO
			
			
			
			

Table footnotes

1. If your answer is the same for all adult groups or all procedures, you can collapse your answer across the groups and/or procedures.

8.4 Non-English-speaking or -reading adult subjects. Will you enroll adult subjects who do not speak English or who lack fluency or literacy in English?

	No
	Yes

→ If yes, describe the process you will use to ensure that the oral and written information provided to them during the consent process and throughout the study will be in a language readily understandable to them and (for written materials such as consent forms or questionnaires) at an appropriate reading/comprehension level.

a. Interpretation. Describe how you will provide interpretation and when. Also, describe the qualifications of the interpreter(s) – for example, background, experience, language proficiency in English and in the other language, certification, other credentials, familiarity with the research-related vocabulary in English and the target language.

b. Translations. Describe how you will obtain translations of all study materials (not just consent forms) and how you will ensure that the translations meet the UW IRB's requirement that translated documents will be linguistically accurate, at an appropriate reading level for the participant population, and culturally sensitive for the locale in which they will be used.

8.5 Barriers to written documentation of consent. There are many possible barriers to obtaining written documentation of consent. Consider, for example, individuals who are functionally illiterate; do not read English well; or have sensory or motor impairments that may impede the ability to read and sign a consent form.

a. Describe your plans (if any) for obtaining written documentation of consent from potential subjects who may have difficulty with the standard documentation process (that is, reading and signing a consent form). Skip this question if you are not obtaining written documentation of consent for any part of your research.

Examples of solutions: Translated consent forms; use of the Short Form consent process; reading the form to the person; excluding individuals who cannot read and understand the consent form.

We will exclude individuals who cannot read or understand the consent form.

8.6 Deception. Will you deliberately withhold information or provide false information to any of the subjects? *Note: "Blinding" subjects to their study group/condition/arm is not considered to be deception.*

	No
--------------------------	----

Yes → If yes, describe what information and why.

Example: you may wish to deceive subjects about the purpose of the study.

We provide a buffet meal and surreptitiously monitor the amount of food consumed. We hope to catch a natural, uninhibited food intake from the buffet, so we will not inform subjects that we are monitoring their food intake (e.g. calories, macronutrients and food selections).

a. Will you debrief the subjects later? (Note: this is not required.)

No

Yes

→ If yes, describe how you will debrief the subjects. Upload any debriefing materials, including talking points or a script, to the **Consent Form and Recruitment Materials SmartForm of Zipline**.

At the 6-month visit research subjects will be debriefed at the end of the visit. Research staff will use a script to inform subjects that the calories in the food eaten during the buffet were monitored. Subjects will be given the opportunity to ask questions and revoke consent for keeping the food intake data.

8.7 Cognitively impaired adults, and other adults unable to consent.

a. **Cognitively impaired adults and other adults unable to consent.** Do you plan to include such individuals in your research?

Examples: individuals with Traumatic Brain Injury (TBI) or dementia; individuals who are unconscious, or who are significantly intoxicated.

No → If no, go to [question 8.8](#).

Yes → If yes, answer the following questions.

a.1. **Rationale.** Provide your rationale for including this population in your research.

a.2. **Capacity for consent / decision making capacity.** Describe the process you will use to determine whether a cognitively impaired individual is capable of consent decision making with respect to your research protocol and setting. If you will have repeated interactions with the impaired subjects over a time period when cognitive capacity could increase or diminish, also describe how (if at all) you will re-assess decision-making capacity and consent during that time.

a.3. **Permission (surrogate consent).** If you will include adults who cannot consent for themselves, describe your process for obtaining permission ("surrogate consent") from a legally authorized representative (LAR).

For research conducted in Washington State, see the [SOP: Legally Authorized Representative](#) to learn which individuals meet the state definition of "legally authorized representative".

a.4. **Affirmation**. Describe whether assent will be required of all, some, or none of the subjects. If some, indicate which subjects will be required to assent and which will not (and why not). Describe any process you will use to obtain and document assent from the subjects.

a.5. **Dissent or resistance**. Describe how you will identify the subject's objection or resistance to participation (including non-verbal) during the research, and what you will do in response.

8.8 Consent-related materials. Upload to the Consent Forms and Recruitment Materials SmartForm of **Zipline** all consent scripts/talking points, consent forms, debriefing statements, Information Statements, Short Form consent forms, parental permission forms, and any other consent-related materials you will use.

- Translations must be included. However, you are strongly encouraged to wait to provide them until you know that the IRB will approve the English versions.
- Combination forms: It may be appropriate to combine parental permission with consent, if parents are subjects as well as providing permission for the participation of their children. Similarly, a consent form may be appropriately considered an assent form for older children.
- For materials that cannot be uploaded: upload screenshots or written descriptions that are sufficient to enable the IRB to understand the types of data that will be collected and the nature of the experience for the participant. You may also provide URLs (website addresses) or written descriptions below. Examples of materials that usually cannot be uploaded: mobile apps; computer-administered test; licensed and restricted standardized tests.

